7.4 INTERIM ANALYSES

In order to ensure the patient's safety during the trial, a partially external DMC, independent of the trial and project teams, will be set-up to review all available safety data as well as selected efficacy data at regular intervals following first-patient-in. A DMC Statistical Analysis Plan (SAP) which describes the analyses required for assessment by the DMC will be produced and finalized prior to first patient screened into the trial. Further details will be provided in a DMC charter.

No formal interim analysis is planned. However a first exploratory analysis of BM data (e.g. RNAseq and inflammatory BMs) may be performed if the period for recruiting of the entire patient population exceeds approximately 6 months. The purpose will be to facilitate further substance development and project planning. The results of these evaluations will be preliminary and may be subject to change, as these do not involve a formal database lock. No interim report will be written. There will be no changes to the design of the trial as a result of the performance of this optional exploratory analysis. If performed, the exploratory analysis of BM data will be done once the first 50% of the total required number of patients has completed 12 weeks of study. Further details of this optional exploratory analysis of BM data will be described in the TSAP.

7.5 HANDLING OF MISSING DATA

Every effort should be made to collect complete data at all visits.

With respect to safety evaluations, it is not planned to impute missing values.

No imputations for the primary endpoint and for any missing BM data are planned.

7.6 RANDOMISATION

No randomisation is planned in this trial, as it is an open-label trial with one treatment arm. All patients will receive the same treatment. A randomisation list will only be provided for logistical reasons with a block size of 1, i.e., a list of consecutive numbers is provided with separate number ranges for each site (starting with number and so on for the different sites).

7.7 DETERMINATION OF SAMPLE SIZE

In line with the exploratory nature of the trial, 10 patients with active UC will be enrolled. The planned sample size is not based on a power calculation but on feasibility, coordinating investigator's experience with regard to recruitment and practical considerations.

If patients withdraw early from treatment prior to Week 12, they may be replaced. Up to 4 patient replacements is considered adequate to ensure that the required number of patients provide data through Week 12.

Page 65 of 82

Proprietary confidential information © 2019 Boehringer Ingelheim International GmbH or one or more of its affiliated companies

8. INFORMED CONSENT, TRIAL RECORDS, DATA PROTECTION, PUBLICATION POLICY

The trial will be carried out in compliance with the protocol, the ethical principles laid down in the Declaration of Helsinki, in accordance with the ICH Harmonized Tripartite Guideline for Good Clinical Practice (GCP), relevant BI Standard Operating Procedures (SOPs), the EU regulation 536/2014 and other relevant regulations.

Standard medical care (prophylactic, diagnostic and therapeutic procedures) remains in the responsibility of the treating physician of the patient.

The Investigator will inform the sponsor immediately of any urgent safety measures taken to protect the trial subjects against any immediate hazard, and also of any serious breaches of the protocol or of ICH GCP.

The BI transparency and publication policy can be found on the following web page: trials.boehringer-ingelheim.com. The rights of the Investigator and of the sponsor with regard to publication of the results of this trial are described in the Investigator contract. As a rule, no trial results should be published prior to finalization of the Clinical Trial Report.

The certificate of insurance cover is made available to the Investigator and the patients, and is stored in the ISF.

8.1 TRIAL APPROVAL, PATIENT INFORMATION, INFORMED CONSENT

This trial will be initiated only after all required legal documentation has been reviewed and approved by the respective Independent Ethics Committee (IEC) and competent authority according to national and international regulations. The same applies for the implementation of changes introduced by amendments.

Prior to patient participation in the trial, written informed consent must be obtained from each patient according to ICH / GCP and to the regulatory and legal requirements of the participating country. Each signature must be personally dated by each signatory and the informed consent and any additional patient-information form retained by the Investigator as part of the trial records. A signed copy of the informed consent and any additional patient information must be given to each patient."

Re-consenting may become necessary when new relevant information becomes available and should be conducted according to the sponsor's instructions.

The consent and re-consenting process should be properly documented in the source documentation.

8.2 DATA QUALITY ASSURANCE

A quality assurance audit/inspection of this trial may be conducted by the sponsor, sponsor's designees, or by IEC or by regulatory authorities. The quality assurance auditor will have

access to all medical records, the Investigator's trial-related files and correspondence, and the informed consent documentation of this clinical trial.

8.3 RECORDS

Case Report Forms (CRF) for individual patients will be provided by the sponsor. For drug accountability, refer to Section 4.1.8.

8.3.1 Source documents

In accordance with regulatory requirements the Investigator should prepare and maintain adequate and accurate source documents and trial records that include all observations and other data pertinent to the investigation on each trial subject. Source data as well as reported data should follow good documentation practices and be attributable, legible, contemporaneous, original and accurate. Changes to the data should be traceable (audit trail). Data reported on the CRF must be consistent with the source data or the discrepancies must be explained.

The current medical history of the subject may not be sufficient to confirm eligibility for the trial and the Investigator may need to request previous medical histories and evidence of any diagnostic tests. In this case the Investigator must make three documented attempts to retrieve previous medical records. If this fails a verbal history from the patient, documented in their medical records, would be acceptable.

If the patient is not compliant with the protocol, any corrective action e.g. re-training must be documented in the patient file.

For the eCRF, data must be derived from source documents, for example:

- Patient identification: gender, date or year of birth (in accordance with local laws and regulations)
- Patient participation in the trial (substance, trial number, patient number, date patient was informed)
- Dates of Patient's visits, including dispensing of trial medication
- Medical history (including surgeries, history of UC and concomitant diseases, if applicable)
- Medication history
- AEs and outcome events (onset date (mandatory), and end date (if available))
- SAEs (onset date (mandatory), and end date (if available))
- Concomitant therapy (start date, changes)
- Originals or copies of laboratory results and other imaging or testing results, with proper documented medical evaluation (in validated electronic format, if available)
- Completion of Patient's Participation in the trial" (end date; in case of premature discontinuation document the reason for it).
- Prior to allocation of a patient to a treatment into a clinical trial, there must be documented evidence in the source data (e.g. medical records) that the trial participant meets all inclusion criteria and does not meet any exclusion criteria. The absence of records (either medical records, verbal documented feedback of the patient or testing

conducted specific for a protocol) to support inclusion/exclusion criteria does not make the patient eligible for the clinical trial.

8.3.2 Direct access to source data and documents

The sponsor will monitor the conduct of the trial by regular on-site monitoring visits and inhouse data quality review. The frequency of on-site monitoring will be determined by assessing all characteristics of the trial, including its nature, objective, methodology and the degree of any deviations of the intervention from normal clinical practice.

The Investigator/institution will allow on-site trial-related monitoring, audits, Institutional Review Board (IRB) / IEC review and regulatory inspections. Direct access must be provided to the eCRF and all source documents/data, including progress notes, copies of laboratory and medical test results, which must be available at all times for review by the CRA, auditor and regulatory inspector (e.g. FDA). The CRA and auditor may review all eCRFs and informed consents. The accuracy of the data will be verified by direct comparison with the source documents described in Section 8.3.1. The sponsor will also monitor compliance with the protocol and ICH GCP.

8.3.3 Storage period of records

Trial site(s):

The trial site(s) must retain the source and essential documents (including ISF) according to the national or local requirements (whatever is longer) valid at the time of the end of the trial. Sponsor:

The sponsor must retain the essential documents according to the sponsor's SOPs.

8.4 EXPEDITED REPORTING OF ADVERSE EVENTS

BI is responsible to fulfil their legal regulatory reporting obligation and in accordance to the requirements defined in this CTP.

8.5 STATEMENT OF CONFIDENTIALITY AND PATIENT PRIVACY

Individual patient data obtained as a result of this trial is considered confidential and disclosure to third parties is prohibited with the exceptions noted below and in 5.5.1. Patient privacy will be ensured by using patient identification code numbers.

Data protection and data security measures are implemented for the collection, storage and processing of patient data in accordance with the principles 6 and 12 of the WHO GCP handbook. Treatment data may be given to the patient's personal physician or to other appropriate medical personnel responsible for the patient's welfare. Data generated as a result of the trial need to be available for inspection on request by the participating physicians, the Sponsor's representatives or delegates, by the IRB / IEC and the regulatory authorities.

8.6 TRIAL MILESTONES

The **start of the trial** is defined as the date of the enrolment of the first patient in the whole trial.

The end of the trial is defined as the date of the last visit of the last patient in the whole trial ("Last Patient Out"). The "**Last Patient Drug Discontinuation**" (LPDD) date is defined as

the date on which the last patient at an individual trial site ends trial medication (as scheduled PP or prematurely). Individual Investigators will be notified of Suspected Unexpected Serious Adverse Reactions

(SUSARs) occurring with the trial medication until 6 weeks after LPDD at their site. **Early termination of the trial** is defined as the premature termination of the trial due to any reason before the end of the trial as specified in this protocol.

Temporary halt of the trial is defined as any unplanned interruption of the trial by the sponsor with the intention to resume it.

Suspension of the trial is defined as an interruption of the trial based on a Health Authority request.

The IEC / competent authority in each participating EU member state will be notified about the trial milestones according to the respective laws.

A final report of the clinical trial data will be written only after all patients have completed the trial in all countries (EU or non-EU) to incorporate and consider all data in the report. The sponsor will submit to the EU database a summary of the final trial results within one year from the end of a clinical trial as a whole, regardless of the country of the last patient (EU or non-EU).

Page 69 of 82

Proprietary confidential information © 2019 Boehringer Ingelheim International GmbH or one or more of its affiliated companies

9. **REFERENCES**

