Pharmacokinetics (PK) analysis showed that exposure (AUC_{0-tz and Cmax}) to BI 655130 seems to increase with increasing dose in a greater than dose-proportional manner from 0.01 to 0.3 mg/kg while exposure increased with increasing dose in an approximately dose-proportional manner from 0.3 to 10 mg/kg. The effective half-life of BI 655130 is approximately 4 weeks in the linear dose range. Overall, PK data so far suggests target-mediated drug disposition kinetics for BI 655130. The saturation of the non-linear elimination pathway is likely occurring after 0.3 mg/kg and BI 655130 seems to exhibit linear kinetics from the next dose-level onwards. Anti-drug antibodies (ADA) were detected in 8 patients, 3 of those had pre-existing levels. However, caution should be taken in interpreting the ADA results because the drug concentrations in many ADA samples exceeded the drug tolerance level of the ADA assay (100 µg/mL). Pharmacodynamic (PD) effects in this first in human Single Rising Dose trial (c03320877) were assessed by indirect target engagement of IL-36R by BI 655130 using an ex-vivo whole blood stimulation assay. Preliminary analyses indicate that >94% peripheral IL-36R receptor occupancy is achieved with doses ≥3 mg/kg from 30 minutes post infusion to Week 10.

Boehringer Ingelheim		03 Apr 2019
BI Trial No.: 1368-0004		_
c10710598-04	Trial Protocol	Page 15 of 82

In the multiple rising dose trial (1368.2), BI 655130 or PBO have been administered to healthy male volunteers at multiple ascending i.v. doses of 3, 6 and 10 mg/kg given once a week (qw) for 4 weeks (i.e. 4 administrations), as well as a single dose cohort of 20 mg/kg. All dose groups (8 patients each, 3:1 on active or PBO) have completed dosing and 4 weeks of follow-up. Overall, BI 655130 was well tolerated. There were no AEs considered to be dose limiting and no SAEs. In all cases the AEs were of mild or moderate intensity. Furthermore, there were no clinically relevant abnormalities on treatment with BI 655130 with respect to safety laboratory, vital signs, or ECGs as assessed by a central reader.

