3. DESCRIPTION OF DESIGN AND TRIAL POPULATION

3.1 OVERALL TRIAL DESIGN AND PLAN

[figure not shown]
This is an open-label, single-arm, phase IIa exploratory trial to assess the genomic and epigenetic changes in both the patient and the microbiome, in response to the IL-36 *signalling* blockade induced by i.v. treatment with BI 655130 in patients with moderate to severe active UC. 10 patients will be investigated.

The trial includes a screening period, a 12-week treatment period and a safety follow-up period of 16 weeks. This allows safety monitoring for 20 weeks (~5 half-lives of BI 655130) after the last dose of BI 655130, which is administered at Week 8.

Patients should be on stable doses of conventional treatment for their disease.

Patients found suitable for trial participation based on in-/exclusion criteria during screening period can enter the treatment phase. Administration of 1200mg BI 655130 intravenously will take place every four weeks (Day 1, Week 4 and Week 8).

A schematic overview of trial design is shown in Figure 3.1: 1.

Abbreviations: W0: Week 0, W4: Week 4, W8: Week 8, W12: Week 12, W28: Week 28, ψ : i.v. infusion

During treatment phase, sequential sigmoidoscopies will be conducted to collect biopsies for evaluation of endpoint variables. Also, blood and stool samples will be collected at various visits, and data will be correlated with the results from biopsies.

Endoscopic as well as histologic evaluations of mucosal biopsies will be performed by a central expert who is independent from the investigator.

Patients who terminate study drug early in trial 1368-0004 will complete EoT visit procedures and return for an End of Observation (EoO) visit 20 weeks (>5 half-lives of BI 655130) after the last dose of BI 655130.

An overview of all relevant trial activities is provided in the Flow Chart. For visit schedules and details of trial procedures at selected visits, refer to Section 6.1 and Section 6.2, respectively.

Patients who complete the full treatment period of study 1368-0004 will be offered to roll over into a long-term extension trial (1368-0017).

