- Additional arguments amongst those stated before, like alternative explanation (e.g. situations where other drugs or underlying diseases appear to provide a more likely explanation for the observed event than the drug concerned).
- Disappearance of the event even though the trial drug treatment continues or remains unchanged.
- 5.3.5.2 Adverse event collection and reporting

AE Collection

The investigator shall maintain and keep detailed records of all AEs in the patient files.

The following must be collected and documented on the appropriate CRF(s) by the investigator:

- From signing the informed consent onwards until the individual patient's end of trial: all AEs (serious and non-serious) and all AESIs.
- After the individual patient's end of trial: the investigator does not need to actively monitor the patient for AEs but should only report related SAEs and related AESIs of which the investigator may become aware of by any means of communication, e.g. phone call. Those AEs should however, not be reported in the CRF.

03 Apr 2019 Page 48 of 82

Proprietary confidential information © 2019 Boehringer Ingelheim International GmbH or one or more of its affiliated companies

[figure not shown]

Figure 5.3.5.2: 1 AE reporting

The residual effect period (REP) for BI 655130, i.e., when measurable drug levels or PD effects are still likely to be present after the last administration, is 140 days (20 weeks). Therefore, all AEs reported through the REP will be considered on-treatment, cf. Section 7.3.4.

As end of REP coincides with EoO visit (last per protocol (PP) visit) in this trial, all AEs reported from first dose until end of the trial will be considered on-treatment.

AE reporting to sponsor and timelines

The investigator must report SAEs, AESIs, and non-serious AEs which are relevant for the reported SAE or AESI, on the BI SAE form via fax immediately (within 24 hours) to the sponsor's unique entry point (country specific contact details will be provided in Section 1 of the ISF). The same timeline applies if follow-up information becomes available. In specific occasions the investigator could inform the sponsor upfront via telephone. This does not replace the requirement to complete and fax the BI SAE form.

With receipt of any further information to these events, a follow-up SAE form has to be provided. For follow-up information the same rules and timelines apply as for initial information.

Information required

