6.2.3 Follow Up Period and Trial Completion

For all patients, termination of trial medication and trial completion must be recorded on the corresponding eCRF.

For patients completing the trial regularly, two safety follow-up visits will be scheduled: 10 weeks (FU1 visit) and 20 weeks (EoO visit) after the last dose of study drug (which is at Week 8, Visit 7).

Early treatment discontinuation

Patients who discontinue treatment prior to the regular EoT visit, EoT procedures should be completed as soon as possible after termination of study drug. These patients should return to the clinic for an EoO visit 20 weeks after their last administered dose of BI 655130.

Further treatment after the end of the trial

At the end of the trial, patients will be treated for their UC at the discretion of the investigator, according to local UC guidelines (e.g. ECCO guideline $\underline{R17-0243}$).

Trial completion:

Trial completion is defined as a patient having reached the EoO visit (Week 28).

Patients who complete regular treatment in study 1368-0004 will be offered to enter a long-term extension trial (1368-0017), which is currently in preparation. These patients can switch to trial 1368-0017 at EoT visit, and for these patients, their EoT visit will also be their EoO visit.

Page 58 of 82

Proprietary confidential information © 2019 Boehringer Ingelheim International GmbH or one or more of its affiliated companies

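### SUSAR notices to investigators end 6 weeks after the site's last patient stops medication, while non-roll-over patients stay in the 20-week residual effect follow-up

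*Protocol*

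**What the plan says.** Protocol section 8.6 sets the period over which individual investigators are told of suspected unexpected serious adverse reactions: "SUSARs) occurring with the trial medication until 6 weeks after LPDD at their site". LPDD is defined there as "the date on which the last patient at an individual trial site ends trial medication (as scheduled PP or prematurely". The definition does not say whether a patient ends medication at the last infusion (Week 8) or at the end of the treatment period (EoT, Week 12).

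Other sections work to a longer period:

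- Section 5.3.5.2 defines the residual effect period (REP). It says that drug levels or pharmacodynamic "effects are still likely to be present after the last administration, is 140 days (20 weeks"), and it counts adverse events in that period as on-treatment. Section 7.3.4 and SAP Table 6.1: 1 use the same 140 days.
- Section 5.3.5.2 also ties the last visit to this period: "As end of REP coincides with EoO visit (last per protocol (PP) visit) in this trial".
- Section 3.1 says of the follow-up: "This allows safety monitoring for 20 weeks (~5 half-lives of BI 655130").
- Section 6.2.3 schedules visits at "10 weeks (FU1 visit) and 20 weeks (EoO visit) after the last dose of study drug", and brings early discontinuers back 20 weeks after their own last dose.

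Section 6.2.3 also makes an exception. Patients who complete treatment are offered trial 1368-0017, and for those who enter it the EoT visit is also the EoO visit.

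**The concern.** The follow-up runs to 20 weeks because the protocol expects that drug or its effects may persist that long. During it the investigator assesses causality (section 5.3.5.2) and can call unscheduled safety visits (section 6.2.2). An unexpected serious reaction in another patient, or in another BI 655130 trial, is the kind of news that would lead a site to look for the same event in its own patients. Section 2.3 describes the compound as first in class and lists other trials running in parallel, so such news could arise elsewhere. Under section 8.6 as written, the commitment to pass it on can lapse well before the site's last patient leaves follow-up. At stake is the safety oversight of those patients.

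**Working it through.** **Inputs.** Half-life: "The effective half-life of BI 655130 is approximately 4 weeks in the linear dose range" (section 1.2). REP: 140 days (5.3.5.2, 7.3.4). Planned days from the Flow Chart: last infusion at V7 = Day 57, EoT = Day 85, FU1 = V7 + 70, EoO = V7 + 141. Notice cut-off: LPDD + 6 × 7 = LPDD + 42 days (8.6).

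**The plan's own figure.** 5 half-lives × 28 days = 140 days = 20 weeks, which reproduces the REP. For a patient treated on schedule, the REP ends on Day 57 + 140 = 197, FU1 is Day 57 + 70 = 127, and EoO is Day 57 + 141 = 198.

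**The site's last patient, on schedule and not rolling over:**

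| | LPDD = last infusion | LPDD = EoT |
|---|---|---|
| Notices stop | 57 + 42 = Day 99 (Week 14) | 85 + 42 = Day 127 (Week 18) |
| Relative to FU1 (Day 127) | 28 days before | same day |
| Relative to EoO (Day 198) | 99 days before | 71 days before |
| REP days without notices | 197 − 99 = 98 | 197 − 127 = 70 |
| Share of REP | 98/140 = 70% | 70/140 = 50% |
| Half-lives since last dose | 42/28 = 1.5 | 70/28 = 2.5 |
| Drug left, 0.5^(half-lives) | about 35% | about 18% |

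The last row is illustrative. It assumes simple first-order decay with a 28-day half-life, which leaves about 3% at 20 weeks. Section 2.3 expects faster clearance in UC, so the true fractions may be lower.

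**Any other patient who stays in follow-up.** Let d be the number of days from that patient's last dose to the site's LPDD. REP days without notices = max(0, 140 − 42 − d) = max(0, 98 − d):

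- d = 0 gives 98 days.
- d = 28 gives 70 days.
- d = 49 gives 49 days (35%).
- d of 98 or more gives none.

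The figures of 70% and 50% therefore belong to the last patient at a site. If that patient stops early, the EoT reading helps less, because section 6.2.3 asks for EoT procedures promptly after stopping. That makes d shorter than 28 days, and the gap moves towards 98.

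**Roll-over patients.** They leave this trial at about Day 85. Notices run to their Day 99 at the earliest on either reading, so they have no gap within this trial.

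**The case against.** The strongest reply is that few patients are affected. The trial plans 10 patients with up to 4 replacements. All who complete treatment are offered the extension, and LPDD waits for the last patient at the site. At some sites nobody may be affected. This stands, and it limits the size of the point. It does not remove it: entry to the extension is optional and open only to completers, and a site's last patient who does not roll over is always affected.

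A second reply is that section 8.6 states one routine commitment and forbids nothing further. Section 8.4 holds the sponsor to its legal reporting duties, section 8.1 provides for re-consent on new information, and a DMC reviews safety data. Whether sites also receive notices through the extension or other trials cannot be seen from these documents. A reader should therefore not infer that investigators would certainly be left uninformed. But none of these provisions is a stated notice of SUSARs to investigators, and none sets a longer period.

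A third reply is that nothing requires the two periods to match: the REP classifies adverse events, and the site's own event collection continues regardless. This is right. The point is a poor alignment of two windows, not a formal contradiction.

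**Conclusion.** The gap is real under both readings of LPDD. For the last patient at a site who does not enter 1368-0017, up to 98 of 140 residual-effect days (70%) follow the end of notices if LPDD is the last infusion, or 70 of 140 (50%) if it is a Week 12 EoT visit. These figures assume visits on their planned days.

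Three stronger readings are tempting but unsupported:

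- **That all patients lose most of their cover.** The cut-off is set by site, and roll-over patients have left before it.
- **That the drug-related adverse event endpoint is distorted.** Section 5.3.5.1 bases causality on many event-level factors, the endpoint is descriptive, and no figure in the documents shows that counts would change.
- **That drug is certainly present for 20 weeks.** The protocol says only that drug or effect is likely to remain.

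This is a small, inexpensive safety improvement that should go into the next amendment. It does not call the trial's design or results into question. Legal notification duties outside the documents were not assessed.

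**What to change.** In protocol section 8.6:

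1. State whether LPDD means the date of the last infusion or the EoT visit.
2. Replace the six-week limit with: *until the last patient at their site has completed the EoO visit of this trial or, for patients not entering 1368-0017, 140 days after their last dose in this trial, whichever is later.*

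The 140-day clause also covers a non-roll-over patient who never attends EoO. Naming the last dose in this trial keeps extension dosing out of the rule. One side effect needs a decision: at a site where every patient rolls over, this wording would end notices at the last EoT (Day 85), earlier than today's Day 99 or Day 127. Keeping six weeks after LPDD as a minimum avoids that.

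The cost is a short change to one section. Notices that the sponsor already prepares go to the same sites for about 14 more weeks (98/7) if LPDD is the last infusion, or about 10 (70/7) if it is EoT. No visit, procedure or treatment rule changes.
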